### **8.1.2. iRECIST For Confirmation of PD in Clinically Stable Patients and Radiologic PD per RECIST v1.1.**

RECIST v1.1 will be applied as the primary criteria for assessment of tumor response (Eisenhauer et al. 2009). The response to immunotherapy may differ from the typical responses observed with cytotoxic chemotherapy, including the following (Wolchok et al. 2009; Nishino et al. 2013):

- Response to immunotherapy may be delayed.
- Response to immunotherapy may occur after progressive disease by conventional criteria.
- The appearance of new lesions may not represent progressive disease with immunotherapy.

Therefore, to adequately characterize additional patterns of response and progression specific to patients treated with immunotherapy, which cannot be captured using conventional criteria such as RECIST v1.1, alternative measures of tumor assessment have been developed. The iRECIST standard was developed by the RECIST working group for the use of modified RECIST version 1.1 in cancer immunotherapy trials (Seymour et al. 2017).

After initial disease progression defined by RECIST v1.1, iRECIST guidelines will be applied in the following tumor assessments. In iRECIST, any new lesions are categorized as measurable or non-measurable. Up to 5 lesions total (up to 2 per organ) can be selected as new lesion-target (NL-T). All other new lesions will be followed as new lesion-non-target (NL-NT). The NL-T sum of diameters will be calculated and recorded separately from the sum of diameters for target lesions identified at baseline.

Tumor response by iRECIST will be classified as confirmed progression (iCPD), or unconfirmed progression (iUPD), or stable disease or response (iSD/iPR/iCR) at all subsequent imaging. The initial tumor scan showing disease progression by RECIST v1.1 will be assigned as unconfirmed progression (iUPD) for overall response.

Progression is considered confirmed (iCPD), if the previous response status was iUPD and any of the following happens:

- For target lesions: any further increase in the previously identified target lesion sum of diameters by 5mm or more after iUPD.
- For non-target lesions: any further increase in the size of previously identified non-target lesion iUPD (the increase doesn't need to meet RECIST v1.1 criteria for unequivocal progression)
- For new lesions:
  - an increase in the NL-T previously identified as iUPD and increase  $\geq 5$ mm in sum of diameter OR
  - any increase for NL-NT OR
  - any appearance of additional new lesions

The overall response remains iUPD, IF

- target lesions were the cause of the initial iUPD AND
- target lesions haven't worsened, but they are still above PD threshold (20% increase from the nadir), AND
- no above factors of iCPD occur.

When progression is considered not unconfirmed, the overall response can become iSD/iPR/iCR instead of iUPD if any of the following criteria are met:

- iCR: Target lesions and non-target lesions have regressed completely AND no new lesions.
- iPR: Target lesions have regressed to  $\geq 30\%$  decrease from baseline (iCR or iPR) AND non-target lesions remain non-iCR/non-iUPD AND no new lesion
- iSD: Target lesions have regressed to  $< 20\%$  increase from nadir AND non-target lesions remain non-iCR/non-iUPD AND no new lesion.

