### **Management Guidelines for Patients Who Have Radiologic Evidence of Progressive Disease by RECIST v1.1**

If a patient is clinically stable at the first radiologic PD by RECIST v1.1 (Eisenhauer et al 2009), the patient may be considered for continuation on the study until progression is confirmed. Confirmation of progression must occur no less than 4 weeks later by iRECIST. For patients to be considered for continuation, the following criteria must **all** be met:

- a. Absence of symptoms and signs indicating clinically significant progression of disease;
- b. No decline in ECOG or Karnofsky performance status;
- c. Absence of symptomatic rapid disease progression requiring urgent medical intervention (e.g., symptomatic pleural effusion, spinal cord compression).

The continuation of treatment after initial radiologic PD takes into consideration the observation that some patients may experience transient tumor flare or pseudo-progression with immunotherapy but could have disease response later. Patients may continue to receive treatment after reconsenting. For patients who meet criteria to continue treatment after initial progression (either awaiting confirmation by iRECIST or have iUPD by iRECIST), reconsenting is required. Patients who receive confirmatory imaging do not need to undergo the next scheduled tumor imaging if it is less than 4 weeks later; tumor assessment will resume at the next

scheduled imaging time point, if clinically stable. Patients will be discontinued from study treatment if disease progression is confirmed by iRECIST (Seymour et al. 2017).

If a patient is clinically unstable, the patient should be discontinued from the study treatment at the first radiological PD by RECIST v1.1. The repeat tumor imaging for confirmation of PD by iRECIST is not required.

Clinical stability is defined as the following (Seymour et al. 2017): no worsening of performance status; absence of signs or symptoms that are associated with clinically significant disease progression; no requirement for intensified management, including increased analgesia, radiotherapy, or other palliative care. Clinical stability is ultimately defined by the treating investigator.

A summary of imaging and treatment guidelines for patients who have first radiologic PD is listed in the table below.

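### The target-lesion rule for iCPD omits the iUPD condition that the non-target and new-target rules carry, and nothing clearly ranks iCPD against iPR or iSD, so one scan can meet both definitions

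*Protocol*

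**What the plan says.** Protocol 8.1.2 starts from RECIST v1.1: "The initial tumor scan showing disease progression by RECIST v1.1 will be assigned as unconfirmed progression (iUPD) for overall response". That first progression may come from target lesions, non-target lesions or a new lesion. At the next scan, progression is confirmed "if the previous response status was iUPD and any of the following happens". The main triggers are:

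- **Target lesions:** "any further increase in the previously identified target lesion sum of diameters by 5mm or more after iUPD".
- **Non-target lesions:** "any further increase in the size of previously identified non-target lesion iUPD".
- **New target lesions (NL-T):** "an increase in the NL-T previously identified as iUPD and increase", with a 5 mm minimum on their sum.

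Any growth of new non-target lesions, or any additional new lesion, also confirms.

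The section then gives a rule for staying at iUPD. It names the cause, "target lesions were the cause of the initial iUPD AND", and it requires that no iCPD trigger is present.

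Last come the definitions that reset the status to iCR, iPR or iSD. iPR needs at least a 30% "decrease from baseline (iCR or iPR) AND non-target lesions remain non-iCR/non-iUPD AND no new lesion". iSD needs a target sum less than 20% above nadir, with the same non-target and new-lesion conditions. Neither contains the no-iCPD line. The sentence introducing these definitions says they apply when progression is *not unconfirmed*.

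On treatment, the management guidelines in 8.1.2 state: "Patients will be discontinued from study treatment if disease progression is confirmed by iRECIST". The imaging and treatment table that follows lets a clinically stable patient with iSD, iPR or iCR continue at the investigator's discretion. SAP 6.7 uses iUPD, iCPD and iBOR to define the iRECIST endpoints, but neither restates nor amends the rule.

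**The concern.** The non-target and NL-T bullets tie confirmation to the lesion that was in iUPD. The target bullet prints no such tie. A patient whose iUPD came only from a new lesion can therefore be confirmed as progressed on a 5 mm change in target lesions that never progressed. If the new lesion has meanwhile gone, the same measurements can satisfy iPR or iSD.

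This is close to the situation for which the protocol added iRECIST: 8.1.2 says that a new lesion may not be true progression under immunotherapy, and gives pseudo-progression as the reason for allowing treatment to continue.

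Two things turn on the label. Treatment is discontinued under iCPD and may continue under iPR or iSD. In the SAP, confirmed progression is an iPFS event dated at the first iUPD. An iUPD followed by iSD or iPR is not an event, and an iPR can count towards iORR, iDCR and iDoR. Protocol 8.1.1 has the investigator determine best response with no independent review, so no central reader would impose one interpretation across sites.

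**Working it through.** The plan gives no figure to reproduce. The check applies the printed rules to target sums in mm.

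**Notation.** B = baseline, N = nadir, U = sum at iUPD, S = sum at the next scan. From 8.1.2:

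- iCPD (target bullet): S − U ≥ 5
- iPR: S ≤ 0.70 × B
- iSD: S < 1.20 × N

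iPR and iSD also need no new lesion and non-target lesions not in iUPD. The cases in A therefore assume that whatever caused the iUPD has resolved.

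**A. iUPD caused by a new or non-target lesion**

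| B | N | U | S | S − U | S vs B | S vs N | Definitions met |
|---|---|---|---|---|---|---|---|
| 100 | 60 | 60 | 65 | 5 | 65/100 − 1 = −35.0% | 65/60 − 1 = +8.3% | iCPD, iPR and the iSD limit |
| 100 | 90 | 90 | 95 | 5 | 95/100 − 1 = −5.0% | 95/90 − 1 = +5.6% | iCPD and iSD |

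With iUPD at Week 9 and the next scan at Week 14, the interval is 5 weeks, inside the 4 to 8 week confirmation window.

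In general, iCPD and iPR can coincide whenever U + 5 ≤ 0.70 × B, and iCPD and iSD whenever U + 5 < 1.20 × N. If the sum at iUPD is the nadir (U = N), the second condition becomes 5 < 0.20 × N, that is N > 25 mm.

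**B. iUPD caused by target lesions**

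Here U ≥ 1.20 × N, so S ≥ 1.20 × N + 5 under iCPD and iSD cannot be met. iPR still can. Take B = 100, N = 40, U = 55, S = 60:

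- At iUPD: 55/40 − 1 = +37.5%, so target lesions caused it.
- Next scan: rise 5 mm (iCPD); 60/100 − 1 = −40% (iPR); 60/40 − 1 = +50% over nadir.

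Adding a cause condition to the target bullet removes the overlap in A but not this one. An order between the classes is needed as well.

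**C. The introducing sentence**

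- As printed, *not unconfirmed* does not give iCPD priority, so the overlaps stand.
- Read as *not confirmed*, iCPD is checked first and each scan has one label. The first case in A is then iCPD, although the sum is 35% below baseline and 8.3% above nadir.

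**D. Measurement noise (illustration only)**

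The documents give no measurement error. Assume no true change and a between-scan SD of the difference in sums of 4, 6 or 8 mm. For N = 60 mm, the 20% limit is 12 mm.

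| Assumed SD | P(rise ≥ 5 mm) = 1 − Φ(5/SD) | P(rise ≥ 12 mm) = 1 − Φ(12/SD) |
|---|---|---|
| 4 mm | 0.106 | 0.001 |
| 6 mm | 0.202 | 0.023 |
| 8 mm | 0.266 | 0.067 |

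**The case against.** **The introducing sentence is a slip.** Read literally, it would open iPR and iSD only after progression had been confirmed, which makes little sense. It also says that these classes replace iUPD, not iCPD, and 8.1.2 lists iCPD, iUPD and iSD/iPR/iCR as alternatives. The likely meaning is *not confirmed*, with iCPD checked first. This is a strong point. A reader might infer that the plan definitely assigns two labels to one scan; the documents do not support that, because the sentence that should set the order cannot be read with certainty. What survives is that the order is not legibly stated, and that under the likely correction the missing cause condition decides the label alone.

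**The word *further* already supplies the condition.** A sum that fell from 100 to 60 mm and then reached 65 mm has increased for the first time. That is a fair reading, but the bullet does not state it, and the non-target bullet also says *further* and still names the iUPD lesion.

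**The contrast between bullets is partial.** The triggers for new non-target lesions and for additional new lesions carry no printed tie either. That is true; the comparison rests on the non-target and NL-T bullets and on the stay-at-iUPD rule.

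**The reach is small.** RECIST v1.1 is the primary criterion, the iRECIST endpoints are exploratory and Protocol 9.1 plans no formal test of response. This limits the statistical weight of the point but leaves the discontinuation rule affected.

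**Conclusion.** The point holds on the printed text, within limits. The target bullet lacks a stated iUPD condition, iPR and iSD lack the iCPD exclusion that the stay-at-iUPD rule has, and the sentence that should order the classes is garbled. The overlap in case A depends on the cause of the iUPD having resolved; case B shows a separate iCPD/iPR overlap without that condition.

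For an affected patient the difference is complete: an iPFS event at the first iUPD and treatment stopped, or no event at that point, a possible iORR response and treatment that may continue. The documents do not allow an estimate of how many patients would be affected.

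Two stronger readings should be resisted. A reader might infer that the main efficacy results are biased. Primary ORR and the RECIST v1.1 endpoints (DCR, DoR, TTR, PFS) do not use iCPD; the reach is discontinuation after first progression and iPFS, iORR, iDoR and iDCR. A reader might also take the 11% to 27% in D as the rate of false confirmation or of conflicting labels. Those figures rest on assumed SDs and give only the chance of a 5 mm rise from noise; a conflict in case A also needs the causing lesion to have gone.

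**What to change.** The confirmation triggers, the stay-at-iUPD and reset rules, the management guidelines and the treatment table in Protocol 8.1.2 must be reconciled:

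1. Correct *not unconfirmed* in the sentence introducing iCR, iPR and iSD.
2. State whether the target bullet applies only when target lesions were themselves in iUPD, as the non-target and NL-T bullets do for their lesions.
3. State an explicit order so that iCPD, iUPD and iSD/iPR/iCR are mutually exclusive. A blanket line that a scan meeting iPR is not iCPD would not do: in case B it would relabel target disease that caused the iUPD and is still growing as a response.
4. Align the management guidelines and the treatment table with the result.
5. Restate the classification in SAP 6.7 and derive iPFS, iORR, iDoR and iDCR from it.

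Which rule should govern stopping treatment is for the sponsor to decide. The cost is a few sentences in the protocol, a short paragraph in the SAP and matching programming. The confirmatory scans and lesion measurements are already planned, so no new scans or data are needed.

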### **Management Guidelines for Patients Who Have Radiologic Evidence of Progressive Disease by RECIST v1.1**

If a patient is clinically stable at the first radiologic PD by RECIST v1.1 (Eisenhauer et al 2009), the patient may be considered for continuation on the study until progression is confirmed. Confirmation of progression must occur no less than 4 weeks later by iRECIST. For patients to be considered for continuation, the following criteria must **all** be met:

- a. Absence of symptoms and signs indicating clinically significant progression of disease;
- b. No decline in ECOG or Karnofsky performance status;
- c. Absence of symptomatic rapid disease progression requiring urgent medical intervention (e.g., symptomatic pleural effusion, spinal cord compression).

The continuation of treatment after initial radiologic PD takes into consideration the observation that some patients may experience transient tumor flare or pseudo-progression with immunotherapy but could have disease response later. Patients may continue to receive treatment after reconsenting. For patients who meet criteria to continue treatment after initial progression (either awaiting confirmation by iRECIST or have iUPD by iRECIST), reconsenting is required. Patients who receive confirmatory imaging do not need to undergo the next scheduled tumor imaging if it is less than 4 weeks later; tumor assessment will resume at the next

scheduled imaging time point, if clinically stable. Patients will be discontinued from study treatment if disease progression is confirmed by iRECIST (Seymour et al. 2017).

If a patient is clinically unstable, the patient should be discontinued from the study treatment at the first radiological PD by RECIST v1.1. The repeat tumor imaging for confirmation of PD by iRECIST is not required.

Clinical stability is defined as the following (Seymour et al. 2017): no worsening of performance status; absence of signs or symptoms that are associated with clinically significant disease progression; no requirement for intensified management, including increased analgesia, radiotherapy, or other palliative care. Clinical stability is ultimately defined by the treating investigator.

A summary of imaging and treatment guidelines for patients who have first radiologic PD is listed in the table below.

### Imaging and Treatment Guideline for Patients who have First Radiologic PD by RECIST v1.1

	Clinically Stable		Clinically Unstable	
	Imaging	Treatment	Imaging	Treatment
First radiologic evidence of PD by RECIST v1.1	Repeat imaging at 4 to 8 weeks to confirm PD by iRECIST	May continue study treatment while waiting for confirmatory scan by iRECIST	Not required; Repeat imaging at 4 to 8 weeks to confirm PD per investigator's discretion only	Discontinue treatment
Repeat tumor imaging confirms PD (iCPD) by iRECIST	No additional imaging required	Discontinue treatment	No additional imaging required	Not applicable
Repeat tumor imaging shows iUPD by iRECIST	Repeat imaging at 4 to 8 weeks to confirm PD by iRECIST. May occur at next regularly scheduled imaging visit	Continue treatment at the investigator's discretion	Repeat imaging at 4 to 8 weeks to confirm PD per investigator's discretion only	Discontinue treatment.
Repeat tumor imaging shows iSD, iPR, or iCR by iRECIST per Investigator assessment.	Continue regularly scheduled imaging assessments.	Continue study treatment at the Investigator's discretion.	Continue regularly scheduled imaging assessments.	Discontinue treatment

Abbreviations: iCPD = iRECIST confirmed progressive disease; iCR = iRECIST confirmed complete response; iSD = iRECIST confirmed stable disease; iUPD = iRECIST unconfirmed progressive disease; PD = progressive disease; RECIST= Response Evaluation Criteria in Solid Tumors.

### 8.1.3. Efficacy Assessment for mCRPC Patients

For mCRPC patients enrolled in this trial (both during dose escalation, Cohorts A and B, and dose expansion Cohorts D1 and D2), response criteria set forth by the Prostate Cancer Clinical Trials Working Group 3 will be utilized (Scher et al. 2016). Efficacy will be evaluated on a combination of RECIST v.1.1 (if patient has measurable disease), prostate-specific antigen (PSA) measurements, and bone scintigraphy using  $^{99m}\text{Tc}$ -methylene diphosphonate radionucleotide ( $^{99m}\text{Tc}$  MDP). Multi-parametric MRI may also be used to evaluate response or progression in bone-only disease. Central measurement of circulating tumor cells is planned at a frequency of every 3 weeks but will not be required for efficacy evaluation.

For patients with measurable disease, RECIST v1.1, as described above in Section 8.1.1, will be utilized with the following caveats:

- I. For nodal lesions, separate pelvic vs extra-pelvic disease and record up to 5 nodal lesions in total.
- II. In order to classify as progression, previously normal lymph nodes (<1 cm) must have grown by at least 0.5 cm in the short axis from baseline scan or nadir and be  $\geq 1$  cm in the short axis.
- III. Nodes that have progressed to  $\geq 1.5$  cm in the short axis are considered measurable; nodes that have progressed to 1 cm to <1.5 cm are considered pathologic but subject to clinical discretion and non-measurable.
- IV. Visceral disease should be designated separately as lung, liver, adrenal, or CNS.

All mCRPC patients will undergo a  $^{99m}\text{Tc}$  MDP scintigraphy at baseline to evaluate skeletal disease involvement. Bone lesions should be evaluated every 9 weeks ( $\pm 7$  days) and can be scheduled around CT/MRI disease staging. Due to possible bone flare that can be part of bone healing in response to treatment, and not actual progression, a 2+2 rule should be used for assessment. Progression should only be called if at least 2 new lesions are seen on the first on-treatment scan, followed by at least 2 additional lesions on the second or subsequent post-treatment scans.

For patients with non-measurable disease, PSA evaluations will be utilized for response assessment to treatment. Prostate-specific antigen will be measured at each treatment cycle (every 3 weeks), but because favorable PSA response to treatment may be delayed, early PSA rises should be ignored until 12 weeks unless patient is rapidly progressing (new lesions on image assessment) with clinical deterioration. After the first evaluation at 12 weeks, PSA response should be evaluated at every 9 weeks for progression. A PSA increase of  $\geq 25\%$  and  $\geq 2$  ng/dL from baseline/nadir, confirmed with a second measurement at least 3 weeks apart, will be considered progression. A PSA decrease from baseline that is  $\geq 50\%$  will be considered a response and should be confirmed with a repeat measurement at least 3 weeks apart.

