#### **9.4.3.2. Secondary Analyses**

The **disease control rate** (DCR), defined as the proportion of patients who achieved a CR or PR or SD) out of all patients treated, will also be summarized. Best response is determined from a sequence of responses assessed. Two objective status determinations of CR before progression are required for a best response of CR. Two determinations of PR or better before progression, but not qualifying for a CR, are required for a best response of PR.

**Duration of response** (DoR) is defined as the time from the date measurement criteria for CR or PR (whichever is first recorded) are first met until the first date that disease is recurrent or objective progression is observed, per RECIST v1.1 criteria, or the date of death from any cause in the absence of objectively determined disease progression or recurrence. Duration of SD will be calculated only for patients with best response of SD. It is measured from the date of start of treatment to the date of first progression of disease or the date of death due to any cause, whichever is earlier. For each patient who is not known to have died or to have had a progression of disease as of the data-inclusion cut-off date, duration of SD will be censored at the date of last objective response assessment prior to the date of any subsequent systemic anticancer therapy.

**Progression-free survival** (PFS) is defined as the time from the date of start of treatment to the first date of the observed clinical or radiologically documented PD or death due to any cause,

whichever occurs first. For patients who are not known to have died or progressed as of the data-inclusion cut-off date, PFS time will be censored at the date of the last objective progression-free disease assessment prior to the date of any subsequent systematic anticancer therapy.

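### As worded, the bone-scan rule for mCRPC gives no way to call progression by scintigraphy when fewer than 2 new lesions are on the first on-treatment scan, however many appear later

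*Protocol*

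**What the plan says.** Protocol Section 8.1.3 covers all mCRPC patients, in Cohorts A, B, D1 and D2. It opens with a general reference: "response criteria set forth by the Prostate Cancer Clinical Trials Working Group 3 will be utilized".

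On bone disease it sets the schedule ("Bone lesions should be evaluated every 9 weeks", with a window of 7 days either side). It then sets a 2+2 rule, and the reason it gives is that early bone flare may reflect healing rather than true progression. The rule has two parts, and both must be met. The first part reads: "Progression should only be called if at least 2 new lesions are seen on the first on-treatment scan". The second part asks that this finding then be "followed by at least 2 additional lesions on the second or subsequent post-treatment scans".

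The section names two other routes. One is imaging: "Multi-parametric MRI may also be used to evaluate response or progression in bone-only disease". The other is PSA in non-measurable disease, where a rise "confirmed with a second measurement at least 3 weeks apart, will be considered progression".

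Protocol Section 9.4.3.2 measures PFS to the "first date of the observed clinical or radiologically documented PD or death due to any cause". The event and censoring table that follows, repeated in SAP Section 6.7, defines adequate assessment by RECIST v1.1 and has no entry for bone-scan or PSA progression.

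**The concern.** Flare is a reason for caution about new lesions on the first on-treatment scan. The sentence goes further: it makes lesions on that scan a precondition for any bone-scan progression at any time. Lesions that first appear later have no flare explanation on the protocol's own reasoning, yet they are the ones that cannot be called.

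The current amendment was written to admit mCRPC patients without measurable disease, and inclusion criterion 11 exempts Cohorts D1 and D2 from the measurable-lesion requirement. For patients with little or no measurable soft-tissue disease, the bone scan is a main means of seeing progression. Cohort D may enrol up to 50 patients. PFS is a secondary endpoint, duration of stable disease is also analysed, and progression is a ground for stopping study treatment under Protocol Section 7.1. Sites applying the sentence literally and sites applying the cited criteria could classify the same scans differently.

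**Working it through.** The plan gives no figure to reproduce: neither document states a median, event count or precision for mCRPC PFS.

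**1. What the rule calls.** Let n1, n2, ... be the new lesions on successive on-treatment scans. Literally, progression is called if n1 ≥ 2 and some later count is ≥ 2.

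| New lesions on scans 1 to 4 | Called? |
|---|---|
| 2, 2, 0, 0 | yes |
| 2, 0, 2, 0 | yes |
| 0, 2, 2, 2 | no |
| 0, 5, 5, 5 | no |
| 1, 9, 9, 9 | no |
| 0, 0, 2, 2 | no |

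The last four rows stay uncalled however long follow-up runs.

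**2. How much bone progression starts after the first scan.** The first scan is due at week 9, or 9 × 7 / 30.4375 = 2.07 months. Assume an exponential time to bone progression with median m months. The share starting after week 9 is exp(−ln 2 × 2.07 / m).

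- m = 3: 62%
- m = 6: 79%
- m = 9: 85%
- m = 12: 89%

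Moving the scan within its window (weeks 8 to 10) gives 59% to 65% at m = 3 and 88% to 90% at m = 12. The medians are assumptions.

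**3. What that could do to PFS.** Further assumptions: bone-scan progression is a PFS event; MRI and PSA rescue no missed case; bone-only and all other PFS events have constant, independent hazards; a fraction s of the total hazard λ is bone-only; bone scans are every 9 weeks. The comparator dates bone progression at the first scan after onset. The literal rule counts it only if onset is by week 9, and the second condition is taken as always met.

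At 26 weeks the scans already done are at weeks 9 and 18, so:

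- comparator: exp(−λ[26(1 − s) + 18s])
- literal rule: exp(−λ[26(1 − s) + 9s])

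with λ = ln 2 / (total median in weeks). For a 6-month total median, λ = 0.6931 / 26.09 = 0.02657. With s = 0.6 the comparator is exp(−0.02657 × 21.2) = 56.9% and the literal rule exp(−0.02657 × 15.8) = 65.7%.

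| Total median | s | Comparator | Literal rule | Rise (points) |
|---|---|---|---|---|
| 3 mo | 0.2 | 27.3% | 30.1% | 2.7 |
| 3 mo | 0.4 | 29.8% | 36.0% | 6.3 |
| 3 mo | 0.6 | 32.4% | 43.2% | 10.8 |
| 4 mo | 0.2 | 37.8% | 40.6% | 2.8 |
| 4 mo | 0.4 | 40.3% | 46.5% | 6.2 |
| 4 mo | 0.6 | 43.0% | 53.3% | 10.3 |
| 6 mo | 0.2 | 52.3% | 54.9% | 2.6 |
| 6 mo | 0.4 | 54.6% | 60.0% | 5.5 |
| 6 mo | 0.6 | 56.9% | 65.7% | 8.8 |

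Rises are taken before rounding. A simulation of 400,000 patients per scenario agrees to within 0.2 points. Its median PFS is unchanged at 3 months with s = 0.2 or 0.4 (14.0 and 15.7 weeks), and moves most at 6 months with s = 0.6 (27.0 to 51.4 weeks).

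**4. DCR.** DCR counts CR, PR or SD as best response, and no minimum SD duration is stated. A patient caught by this wording had no bone-scan progression at week 9. If free of progression otherwise, the patient already counts as disease control; a call at week 18 would not reverse that.

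**The case against.** The strongest reply is that the sentence is a flare safeguard inside a section that adopts the Working Group 3 criteria, and that a sensible site would use those criteria for later lesions. That may happen in practice, but the cited source is not part of the documents. A general reference also does not displace an explicit *only*; if the two differ, the section conflicts with its own reference.

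The second reply is that other routes to progression remain, and this stands in part. MRI is available, but it is optional, limited to bone-only disease and has no threshold. The PSA rule is written for non-measurable disease. CT or MRI under RECIST v1.1 and death apply to everyone. What is blocked is a call by scintigraphy, not every route. A patient with stable measurable soft tissue and new lesions visible only on scintigraphy at week 18 falls outside the MRI and PSA routes as written.

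The third reply is that the link to PFS is not established, and this stands. The objectives assess PFS by RECIST v1.1, and the event table is tied to RECIST v1.1. The text definition includes clinical progression, but a footnote excludes symptomatic deterioration not confirmed by RECIST. If bone-scan progression is not a PFS event, the wording has no effect on PFS.

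Finally, the Phase 1b primary efficacy endpoint is ORR, no formal test of response is planned, and the rule applies equally to D1 and D2. The stake is the accuracy of secondary estimates and consistent classification, not a false positive test.

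**Conclusion.** The defect is in the stated rule: under its plain wording, new bone lesions first appearing after the first on-treatment scan cannot be called as progression by scintigraphy, and neither document supplies another rule for them. Bone progression can be delayed or missed, most of all where there is little or no measurable soft tissue. If bone-scan progression is a PFS event, the effect is to lengthen PFS and duration of stable disease.

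A reader might infer three stronger things, none of which the documents support:

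- *That PFS is inflated outright.* This depends on bone-scan progression being a PFS event, which is left open.
- *That DCR is raised too.* It is not, because the affected patients already qualify at week 9.
- *That the 62% to 89% is the size of the bias.* It is the share of bone progressions starting after week 9 under assumed medians of 3 to 12 months, before competing events.

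The closest thing to a size is the 6-month PFS rise of about 2.5 to 11 points. It rests on total medians of 3 to 6 months, a bone-only share of 20% to 60%, bone-scan progression counting, and no MRI or PSA rescue. None of these values comes from the documents.

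**What to change.** - In Protocol Section 8.1.3, limit the flare sentence to lesions first seen on the first on-treatment scan.
- Reconcile the section with the Working Group 3 criteria it cites, so that lesions first appearing on a later scan have a stated rule for calling, confirming and dating progression. Because progression also leads to stopping treatment, the content of that rule, including the reference scan, is for the sponsor to settle against the cited criteria.
- State in the PFS event tables of Protocol Section 9.4.3.2 and SAP Section 6.7 whether bone-scan progression is a PFS event. The SAP needs its own update: Version 1 rests on protocol amendment (a), before Section 8.1.3 was added.

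The cost is a few sentences in the protocol and a row in each table. No extra scans or visits are needed.
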